## 1. Sample Size Calculation

An a priori power analysis in G\* power with an effect size of 0.5 (Kennedy et al., 2003; Kennedy et al., 2004) indicated that a sample of 130 participants (65 per group, placebo and treatment respectively) with a 10% attrition rate would be necessary to achieve a power level of 0.80 at a significance level of 0.05. Similar trials investigating mood and cognition have shown a change from baseline following an acute dose of lemon balm beginning with changes first observed after 1h and maintained throughout the test day, in samples as small as 18 participants (Kennedy et al., 2004).

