### 2. Recruitment and screening

Participants will be recruited using opportunity sampling. The study will be advertised through email distribution and with posters across the University of Reading and on online social media platforms. Before interested participants are enrolled in the trial, a brief pre-screen video call will be undertaken alongside completion of an entry stress test (PSS). Once pre-screened, participants will be invited to a screening session to determine if they meet additional eligibility criteria regarding habitual diet and general health and lifestyle (examples include willingness to not consume alcohol or coffee prior to the test session and on the test day, or regular exercise levels deemed as excessive, any restrictive diet, no smoking or consuming nicotine-based products 7 days prior to the test session). The visit will also provide an opportunity to become familiar with the mood and cognitive test batteries to be completed at specific timepoints (baseline (0h), 1h, 3, and 5h timepoints) on the test day. If eligible, participants will be invited to attend a test visit the following week. Participants will be compensated with £75 for completing all phases of the study.

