## 4. Testing protocol

#### Test visits

- Participants will be asked to follow a low polyphenol diet for 48hours and restrict caffeine and alcohol intake 24 hours prior to test visits.
- At the screening visit participants will have a chance to complete the various cognitive and mood tasks that will be delivered at various timepoints on the test day.
- On arrival of the acute test day, participants will be randomly assigned to treatment: 300mg lemon balm or placebo condition.
- Adverse events and vital signs (bp, HR) will be recorded to estimate tolerance.

- Participants will consume a standardised breakfast (2 croissants and a glass of water) and complete the first block of cognitive and mood tasks between 8am-9am.
- After the baseline (0h), participants will complete the same cognitive and mood tasks at specific timepoints (1h following supplementation, 3h and 5h) and will receive a standardised lunch (cheese sandwich with a packet of crisps).

The screening session should take no longer than 3 hours, and the acute test day should take no longer than 6 hours spread out over an 8-hour window (8am-4pm). Participants may withdraw at any time without giving any reason. In addition, a participant will be withdrawn from the study if they request discontinuation, exhibit a serious adverse event to any component of the test product, the participant significantly violates the exclusion or inclusion criteria, an illness emerges and/or opinion is that withdrawal is appropriate.

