# Primary Outcome Variable

To determine the effect of 300 mg lemon balm on ratings of calmness following a period of cognitive demand, measured using a 9-point Likert Scale, at baseline (0h) and 5 hours post administration. This Calmness 9-point Likert scale is scored from 1, "Not at all Calm" to 9, "Extremely Calm" Calmness Anchor points.

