### **Analysis**

Before analysis, all data will be checked for assumptions of parametric testing, including Normal distribution, then assessed with boxplots to screen for any outliers. On recommendation of a statistician, all repeated measures data will be analysed using Linear Mixed Modelling (LMM) in RStudio v4.0. This technique can be used to model variance relating to both fixed parameters such as experimental doses and random parameters such as individual differences between subjects, within multiple layers of the same model. Models will be adjusted for potential predictive factors, such as sex, diet quality, physical activity level and severity of baseline stress complaints and/or baseline performance on cognitive tasks where the inclusion of these covariates improves the fit of the model, as long as assumptions are met. Subjects will be included as a random factor as a way of controlling for non-independence of data from the same subjects. The models will be applied in a systematic way to retain consistency between analyses. Where possible, an unstructured covariance matrix will be specified for the repeated observations on a subject within the same period. As LMMs do not require balanced data, subjects with missing data points will not be excluded from the analyses. Post-hoc Bonferroni-corrected parametric tests such as independent t-tests will be performed to estimate between-group differences between placebo and intervention groups, or within-group differences between time points, where appropriate.

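### The stated inputs do not reproduce 130 participants with 10% attrition at 0.80 power; on the standard reading, 130 is essentially the number before attrition

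*Combined protocol and SAP*

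**What the plan says.** The only statement of power is in section 1 (Sample Size Calculation). It reports a G*Power calculation "with an effect size of 0.5" and concludes that "a sample of 130 participants (65 per group, placebo and treatment respectively) with a 10% attrition rate would be necessary". The target is 80% power with alpha set at 0.05. The section gives no test, sidedness, effect-size metric (d or f), within-person correlation or number before attrition. Nor does it say whether 130 counts people enrolled, randomised or evaluable.

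Four other places bear on how the figure should be read:

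- Section 2 (Recruitment and screening): "If eligible, participants will be invited to attend a test visit the following week". There is a gap of about a week between screening and the test day.
- Section 4 (Test visits): "On arrival of the acute test day, participants will be randomly assigned to treatment". Randomisation follows that gap.
- Section 5, Primary Outcome Variable: "To determine the effect of 300 mg lemon balm on ratings of calmness following a period of cognitive demand", rated at baseline and at 5 hours on the same day.
- Section 5, Analysis: "all repeated measures data will be analysed using Linear Mixed Modelling (LMM) in RStudio v4.0", with covariates added only "where the inclusion of these covariates improves the fit of the model". Independent t-tests appear there only as post-hoc comparisons.

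**The concern.** An effect size of 0.5 with 0.80 power and a 0.05 level is a familiar combination. With a two-sided two-sample t-test it gives 64 per group before any allowance for loss. The plan's 65 per group is almost that number, yet the sentence presents it as including 10% attrition. Ten per cent of 130 is 13 people, and one more per group than the minimum cannot absorb that.

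At stake is whether the claimed 0.80 holds before or after the stated loss, and the plan does not say. The timing of the loss decides it. People who drop out in the week between screening and the test day have not been randomised and do not reduce 65 randomised per group. People lost between randomisation and the 5h rating do.

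**Working it through.** **Inputs from section 1:** effect size 0.5; level 0.05; power 0.80; 130 in total, 65 per group; attrition 10%.

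**Assumed, because not stated:** two-sample t-test, two-sided, effect size read as Cohen's d.

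**Step 1. Number needed before attrition.** The normal approximation is n per arm = 2(z₀.₉₇₅ + z₀.₈₀)²/d² = 2(1.960 + 0.842)²/0.25 = 62.8, so 63. The exact noncentral t calculation gives 63.8, so 64 per arm and 128 in total. The plan's 130 matches this to within 2.

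**Step 2. Number needed with 10% attrition.** 128/0.9 = 142.2, which becomes 144 with equal arms. The shortcut of multiplying by 1.1 gives 140.8. Neither is 130.

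**Step 3. Power at the plan's own number.** Power comes from the noncentral t distribution with n₁ + n₂ − 2 degrees of freedom and noncentrality d√(n₁n₂/(n₁ + n₂)). For 65 + 65 the noncentrality is 0.5√32.5 = 2.850. For 59 + 58 it is 0.5√(3422/117) = 2.704.

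| Evaluable | Lost from 130 | Power |
|---|---|---|
| 65 + 65 = 130 | 0 | 0.808 |
| 64 + 64 = 128 | 2 | 0.802 |
| 64 + 63 = 127 | 3 | 0.798 |
| 62 + 62 = 124 | 6 (4.6%) | 0.789 |
| 59 + 58 = 117 | 13 (10%) | 0.765 |

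On this reading 0.80 survives 2 losses, not 13. With 117 evaluable, 80% power is reached at d = 0.52.

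**Step 4. Other readings that use only the stated figures.**

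- One-sided t-test, d = 0.5: 51 per arm, 102 in total; 102/0.9 = 113.3, so about 114.
- Effect size 0.5 read as f in a two-group ANOVA: 34 in total; 34/0.9 = 37.8, so 38.

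Neither gives 130 before or after attrition.

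**Step 5. Calculations that do come near 130, and the extra input each needs.**

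- Baseline-adjusted comparison with a 0h–5h correlation of 0.3: the effective d is 0.5/√(1 − 0.3²) = 0.524, which needs 118; 118/0.9 = 131.1 and 118 × 1.1 = 129.8. The correlation is not in the documents.
- Repeated-measures between-group test with f = 0.25, two measurements and correlation 0.8: 116; 116/0.9 = 128.9. Neither this test nor the correlation is stated.
- One-sided Mann-Whitney test at minimum efficiency (0.864): 118; 118 × 1.1 = 129.8. Neither the test nor the sidedness is stated.

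**The case against.** The strongest reply is that this is an omission rather than a wrong number. The t-test is assumed, the planned main analysis is a mixed model, and at least three calculations land near 130 with attrition included. That stands in part. It means 130 cannot be called wrong under every analysis. It does not make the figure reproducible, because each of those calculations needs an input that the reader would have to guess.

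A second reply is that loss may be small or may fall where it does no harm. Participants are randomised on arrival and rated 5 hours later, and payment is for completing all phases. Nothing in the documents points to 13 people leaving within those hours. This also stands. If the 10% is lost between screening and the test day, 65 per group are still randomised and power is 0.808. But section 1 does not say so, and gives no larger number of eligible people to cover such a loss.

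A third reply is that the mixed model keeps participants with missing data. That does not restore the power by itself. The primary outcome is defined at 0h and 5h only, so someone lost before the 5h rating has no post-dose value of it.

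A reader might go further and infer that the trial is underpowered. The documents do not support this. With 117 evaluable and d standardised on the 5h SD, power is 0.80 or 0.87 for a baseline-adjusted comparison (correlation 0.3 or 0.5), and 0.62 or 0.76 for change from baseline at the same correlations. The correlation and the scale of the effect size are both unstated, so this range shows that power is undetermined. The 0.62 is not evidence of a deficit.

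**Conclusion.** The point holds in a limited form: the sample size and power in section 1 are not reproduced by the inputs given there. On a two-sided two-sample t-test with d = 0.5, 130 is essentially the requirement before attrition (128), against about 142 to 144 with it.

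The practical size is modest. If all 10% is lost after randomisation, power is 0.765 instead of 0.80, a shortfall of about 3.5 points. At roughly 5% same-day loss the shortfall is about 1 point, and it is nil if the loss precedes randomisation. These figures rest on the assumed test, sidedness and metric. The finding that the inputs are incomplete does not. It should be fixed, because this is the only justification of the sample size and the correction is cheap.

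**What to change.** Restate the figure in section 1, naming the test, the sidedness and the effect-size metric, and giving the randomised and evaluable numbers separately. If the t-test reading is right, either of these would do:

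- (a) *130 randomised; if 10% are lost before the 5h rating, 117 evaluable give 76% power for d = 0.5 (80% for d = 0.52), two-sided alpha 0.05, unadjusted t-test.*
- (b) *130 evaluable give 81% power for d = 0.5, two-sided; this number includes no attrition allowance.* The 10% is then removed from the sentence.

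If a different G*Power calculation was used, report that one with all its inputs, including any assumed correlation, and the number before attrition.

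If the 10% means loss between screening and the test day, say that 65 per group are randomised and that about 144 to 146 people eligible after screening are needed (130/0.9 = 144.4; 146 for an even split), with screen failures additional.

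The cost is one or two sentences. Options (a) and (b) add no participants; the screening-loss version adds none randomised but needs more eligible people. The downside is a slightly less favourable stated power, or an open admission that there is no attrition allowance. Raising the number randomised to 144 is not required by this point. If the sponsor chose it, the 14 extra participants would cost at most 14 × £75 = £1,050 in payments, since payment is for completing all phases, plus staff time.

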### 2. Recruitment and screening

Participants will be recruited using opportunity sampling. The study will be advertised through email distribution and with posters across the University of Reading and on online social media platforms. Before interested participants are enrolled in the trial, a brief pre-screen video call will be undertaken alongside completion of an entry stress test (PSS). Once pre-screened, participants will be invited to a screening session to determine if they meet additional eligibility criteria regarding habitual diet and general health and lifestyle (examples include willingness to not consume alcohol or coffee prior to the test session and on the test day, or regular exercise levels deemed as excessive, any restrictive diet, no smoking or consuming nicotine-based products 7 days prior to the test session). The visit will also provide an opportunity to become familiar with the mood and cognitive test batteries to be completed at specific timepoints (baseline (0h), 1h, 3, and 5h timepoints) on the test day. If eligible, participants will be invited to attend a test visit the following week. Participants will be compensated with £75 for completing all phases of the study.

# 3. Randomisation and Blinding Process

A researcher not involved in recruitment or data collection will used blocked randomization with random permuted blocks of two and six individuals to form the allocation list for the two comparison groups of equally balanced males and females weighted across placebo and intervention conditions. The allocation sequence will be concealed to the researchers enrolling and assessing participants. These randomisation codes will be pre-labelled onto opaque containers containing identical pink coloured capsules (intervention and placebo, respectively) and prepared by researcher personnel not involved in the conduct of the trial. On the test day, the investigator running the visit will administer a capsule from the correct container in accordance with the randomisation schedule.

## 4. Testing protocol

#### Test visits

- Participants will be asked to follow a low polyphenol diet for 48hours and restrict caffeine and alcohol intake 24 hours prior to test visits.
- At the screening visit participants will have a chance to complete the various cognitive and mood tasks that will be delivered at various timepoints on the test day.
- On arrival of the acute test day, participants will be randomly assigned to treatment: 300mg lemon balm or placebo condition.
- Adverse events and vital signs (bp, HR) will be recorded to estimate tolerance.

- Participants will consume a standardised breakfast (2 croissants and a glass of water) and complete the first block of cognitive and mood tasks between 8am-9am.
- After the baseline (0h), participants will complete the same cognitive and mood tasks at specific timepoints (1h following supplementation, 3h and 5h) and will receive a standardised lunch (cheese sandwich with a packet of crisps).

The screening session should take no longer than 3 hours, and the acute test day should take no longer than 6 hours spread out over an 8-hour window (8am-4pm). Participants may withdraw at any time without giving any reason. In addition, a participant will be withdrawn from the study if they request discontinuation, exhibit a serious adverse event to any component of the test product, the participant significantly violates the exclusion or inclusion criteria, an illness emerges and/or opinion is that withdrawal is appropriate.

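### Treatment is assigned on arrival, and the withdrawal rule can then remove randomised participants before the 5h primary rating; allocating just before the capsule and keeping later violators in follow-up and analysis would avoid most of this loss.

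*Combined protocol and SAP*

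**What the plan says.** All references are to the combined protocol and SAP.

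- **Timing of allocation (section 4, Test visits).** "On arrival of the acute test day, participants will be randomly assigned to treatment: 300mg lemon balm or placebo condition". This item is listed ahead of the standardised breakfast and the first block of tasks.
- **Withdrawal (section 4, closing paragraph).** Besides the participant's own request and a serious adverse event, the grounds for withdrawal include that "the participant significantly violates the exclusion or inclusion criteria, an illness emerges and/or opinion is that withdrawal is appropriate". The rule does not distinguish people who have been randomised from people who have not.
- **When eligibility is settled (section 2).** It is settled at the pre-screen call and the screening session: "If eligible, participants will be invited to attend a test visit the following week". One listed condition is "no smoking or consuming nicotine-based products 7 days prior to the test session". Alcohol and coffee appear as "willingness to not consume alcohol or coffee prior to the test session and on the test day".
- **Pre-visit instructions (section 4).** "Participants will be asked to follow a low polyphenol diet for 48hours and restrict caffeine and alcohol intake 24 hours prior to test visits". These are not called eligibility criteria.
- **Concealment (section 3).** The sequence is concealed from those enrolling and assessing, and the capsules look identical.
- **Primary outcome (section 5, Primary Outcome Variable).** A 9-point calmness rating, taken at 0h and 5h only.
- **Missing data (section 5, Analysis).** In the mixed model, "subjects with missing data points will not be excluded from the analyses". No analysis population is defined.

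**The concern.** Allocating on arrival opens a gap between randomisation and the capsule in which a participant can be found ineligible and withdrawn. Each such person has used a place on the allocation list without being dosed. Assigning the container a little later would have avoided the loss entirely.

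After dosing the question is different. The rule allows withdrawal for an eligibility violation that comes to light, for illness, or on opinion, and does not say whether the 5h rating is still collected. Illness and opinion are judgements made after the capsule has been taken, so they could be related to treatment. If those participants have no 5h rating, the comparison rests on a subset that randomisation no longer fully protects.

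The sample has little room for either kind of loss, because 65 per group only just exceeds the number needed for 80% power.

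**Working it through.** **1. Can a violation surface after allocation?** Set the stated conditions against the moment of allocation:

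| Condition | Where stated | Can it be settled at screening? |
|---|---|---|
| Stress score, health, age, habitual diet, exercise, medication, task performance | Sections 2 and 5 | Yes, it is a pre-screening or screening criterion |
| Alcohol and coffee | Section 2 | Yes, it is framed as willingness |
| 48h diet; 24h caffeine and alcohol | Section 4 | It is an instruction, not a stated criterion |
| No nicotine for 7 days before the test session | Section 2 | No, the period ends at the test session |

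Screening takes place in the week before the test visit, so compliance with the nicotine condition cannot be fully confirmed until the test day. Allocation is the first thing described on arrival, and the plan describes no check ahead of it.

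**2. What does a withdrawn participant contribute to the primary outcome?**

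- Withdrawn before the 0h block: no rating, so nothing.
- Withdrawn between 0h and 5h: a baseline rating only. The mixed model keeps the person, but a baseline value with no post-dose value carries essentially no information about the treatment effect.
- Violation found after the 5h rating: the rating exists. No rule deletes it, and no rule commits to using it.

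**3. Power.** Inputs from section 1: effect size 0.5 (read as a standardised mean difference), significance level 0.05, target power 0.80, 65 per group. Sidedness is not stated; two-sided is assumed.

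For n per group, power = P(|T| > t\*), where T is noncentral t with 2n − 2 degrees of freedom and noncentrality 0.5 × √(n/2), and t\* is the two-sided 5% critical value.

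The plan's own figure first: 80% power needs 64 per group, or 128 evaluable. The planned 130 agrees with this only if the 10% attrition is left out. With it, 64 / 0.9 = 71.1, so 72 per group or 144. That shortfall is a separate matter and is not counted here.

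The number of losses of the present kind is not stated. As an assumption, take 3-8%:

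- 3% × 130 = 3.9, about 4 people, leaving 126, or 63 per group
- 8% × 130 = 10.4, about 10 people, leaving 120, or 60 per group

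| n per group | Noncentrality | Power |
|---|---|---|
| 65 | 0.5 × √32.5 = 2.850 | 80.8% |
| 64 | 0.5 × √32 = 2.828 | 80.2% |
| 63 | 0.5 × √31.5 = 2.806 | 79.5% |
| 60 | 0.5 × √30 = 2.739 | 77.5% |

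The assumed losses, split equally between groups, cost about 1 to 3 percentage points. Losing two per group is enough to go below 80%.

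**The case against.** The other side has several fair points.

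- **Most criteria are settled before the test day.** A reader might infer that eligibility in general can be verified only on the test day. The plan does not support that. Alcohol and coffee are assessed as willingness, the 48h diet is an instruction, and the rest belongs to screening. Only the nicotine condition clearly fits. This limits the likely number of violations but does not remove the route.
- **No test-day check is described.** The order of allocating, then checking, then withdrawing is therefore an inference, and the withdrawal rule can also act before randomisation. That is correct. Still, with allocation on arrival, the text provides no step at which a check would come first.
- **Withdrawal from the study is not exclusion from the analysis.** A reader might infer that the plan prescribes a completer analysis. It does not. It keeps subjects with missing data, and nothing tells the analyst to discard a 5h rating already given. What stands is narrower: for anyone withdrawn before 5h, keeping them in the model recovers essentially nothing for the primary outcome.
- **Pre-dose losses should not depend on group.** Concealment and identical capsules make this convincing, so a claim of bias from pre-dose removal would go too far. The argument does not reach withdrawals made after dosing for illness or on opinion, and moving the allocation step does not help with those.
- **The size is small and assumed.** True. The larger fall, to 76.5% with 10% loss from 65 per group, comes from the attrition allowance and would exist whenever allocation took place. It should not be charged to this point.

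**Conclusion.** The point holds in limited form. The plan randomises earlier than it needs to, its withdrawal rule covers randomised participants without exception, and a person withdrawn before 5h is effectively lost to the primary comparison. Before dosing, the consequence is mainly lost precision. After dosing, some bias is possible if withdrawal for illness or on opinion is related to treatment, but the documents give no basis for estimating its size.

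On the assumed 3-8% loss, power falls from 80.8% to between 79.5% and 77.5%. This rests on a two-sided test, a standardised difference of 0.5 and equal loss in both groups. The change is worth making because it costs almost nothing, not because the trial's result is in serious jeopardy without it.

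**What to change.** 1. **Section 4, test-day order.** Confirm test-day eligibility and complete the 0h block first. Assign the next numbered container only immediately before the capsule is given. Anyone found ineligible before that point is not randomised, and the container goes to the next participant. The time of intake does not change.
2. **Section 4, after allocation.** State that an eligibility violation discovered later does not by itself end outcome collection. The 5h rating is still taken where the participant is willing and there is no safety reason to stop. Withdrawals for safety remain as written.
3. **Section 5, Analysis.** State that the primary analysis includes all randomised participants in their allocated group, with every available 5h rating. Excluding violators is a sensitivity analysis only.

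The cost is one re-ordered step on the test day and a few sentences of text. The containers are already pre-labelled, so no new supplies are needed. The one downside is that a few violators stay in the primary analysis and may slightly dilute the effect. The change does not recover a 5h rating from someone withdrawn after dosing for safety or at their own request.
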